9.4.3.2. Pharmacokinetic Analyses

PK data analyses will include descriptive summary statistics of the pre-dose and post-dose serum concentrations of elranatamab by study visit and time point. In addition, the PK data from this study may be used to develop a population PK model. The correlations between elranatamab exposure parameters and pharmacodynamic biomarker, efficacy and/or safety outcomes will be explored if data allows. The results of these modeling analyses will be reported separately from the clinical study report.

9.4.3.3. Immunogenicity Analyses

For immunogenicity data, the percentage of patients with positive ADA will be summarized. Listings and summary tabulations of the ADA data at baseline and post-randomization will be generated. Samples may also be analyzed for the presence of NAb, and any data will be similarly summarized. For patients with positive ADA or NAb, the magnitude (titer), time of onset, and duration of ADA or NAb response will also be described, if data permit. The potential impact of immunogenicity on PK and clinical response including pharmacodynamic markers, safety/tolerability and efficacy will be explored, if warranted by the data.

9.4.4. Exploratory Endpoint(s)

The details of exploratory endpoint analyses, including PROs, will be described in the SAP.

Results from exploratory analyses will be reported in the CSR where possible. However, given the exploratory nature of the objective and endpoints, the analyses may not be completed at the time of CSR preparation. If results of exploratory endpoint analyses cannot be included in the CSR, they will be disseminated as appropriate to the scientific community through presentation at scientific meetings and/or publication in peer-reviewed scientific journals.

9.4.5. Other Safety Analyses

The Safety Analysis Set will be the primary population for evaluating safety.

9.4.5.1. Adverse Events

AEs (except CRS and ICANS) will be graded by the investigator according to NCI CTCAE Version 5.0 and coded using MedDRA. CRS and ICANS will be assessed by the investigator according to the grading described by Lee et al (Lee et al, 2019b) (See Section 10.11) and coded using MedDRA. AEs will be characterized by type, frequency, severity, timing, seriousness, and relationship to elranatamab. AEs will be presented with and without regard to causality based on the investigator's judgment. The frequency of overall toxicity, categorized by toxicity Grades 1 through 5, will be described. Additional summaries will be provided for AEs that are observed with higher frequency and for AESIs identified in Section 8.3.8, including CRS and ICANS.

9.4.5.2. Laboratory Test Abnormalities

Clinical laboratory data will be classified by grade according to NCI CTCAE version 5.0 and will be analyzed using summary statistics. The worst on-treatment grades during the treatment period will be summarized. Shifts in toxicity grading from baseline to highest grade during the on-treatment period will be displayed. Results for laboratory tests that are not part of NCI CTCAE will be presented as below, within, or above normal limits. Only participants with post-baseline laboratory values will be included in these analyses. Further details of analyses for all the laboratory parameters will be provided in the SAP.

9.4.5.3. Electrocardiogram Analyses

Changes from baseline for the ECG parameters QT interval, heart rate, QTcF interval, PR interval, and QRS complex will be summarized by cohort and time.

The number (%) of participants with maximum postdose QTcF values and maximum increases from baseline in the following categories will be tabulated by treatment:

Safety QTcF Assessment

Degree of Prolongation	Mild (msec)	Moderate (msec)	Severe (msec)
Absolute value	≥450-480	>480-500	>500
Increase from baseline		30-60	>60

9.4.6. Other Analyse(s)

Pharmacogenomic or biomarker data from Banked Biospecimens may be collected during or after the trial and retained for future analyses; the results of such analyses are not planned to be included in the CSR.

9.5. Interim Analyses

Interim analyses will be performed to assess futility and/or efficacy as described in details below. Participants may be discontinued from the study intervention/study as a result of interim analysis outcome, as described in Section 7. Interim analysis results may be used for decisions regarding stopping for futility, stopping for early success, or adapting the study after the interim analysis.

Before any interim analysis is performed, the details of the objectives, decision criteria, dissemination plan, and method of maintaining the study blind as per Pfizer's SOPs will be documented and approved in the EDMC charter. In addition, the analysis details will be documented and approved in the SAP.

9.5.1. Interim Analysis for Futility and Efficacy

An IA for both (non-binding) futility and efficacy will be conducted on ORR by BICR for Cohort A based on the first 90 participants enrolled and treated in that cohort. At the IA for Cohort A, if there are ≤ 31 (34.4%) objective responders by BICR observed, accrual may be stopped for further evaluation due to futility; if there are ≥ 38 (42.2%) objective responders by BICR observed, the efficacy boundary will be crossed; if the IA crosses neither the futility boundary nor the efficacy boundary, Cohort A will proceed as planned to the final analysis as described in Section 9.2. If the efficacy boundary is crossed, enrollment to the study will continue up to the specified number of participants for the final analysis, and all ongoing participants will continue with scheduled visits per the SoA.

An IA for (non-binding) futility and efficacy will be conducted on ORR by BICR for Cohort B based on the first 30 participants enrolled and treated in that cohort. At the IA for Cohort B, if there are ≤ 3 (10.0%) objective responders by BICR observed, accrual may be stopped for further evaluation due to futility; if there are ≥ 11 (36.7%) objective responders by BICR

observed, the efficacy boundary will be crossed; if the IA crosses neither the futility boundary nor the efficacy boundary, Cohort B will proceed as planned to the final analysis as described in Section 9.2. If the efficacy boundary is crossed, enrollment to the study will continue up to the specified number of participants for the final analysis, and all ongoing participants will continue with scheduled visits per the SoA.

Each respective interim analysis will occur no earlier than the point at which all early responders (ie, those who respond within the first 3 post-baseline assessments) among the participants to be included have had their responses confirmed. At the time of the interim analysis, the testing rule will depend on the actual number of participants included in the analysis for each cohort with sufficient follow-up.

At the time of the SAP amendment prior to the interim analysis, 94 Cohort A participants were initially dosed at least 4 months prior to the data cutoff and were to be included in the interim analysis. The updated boundaries were ≤ 33 (35.1%) objective responders by BICR for futility and ≥ 41 (43.6%) objective responders by BICR for efficacy. It was determined no interim analysis will be performed for Cohort B participants as not enough participants have adequate follow-up since Cohort B has a higher incidence of EMD at baseline compared to Cohort A. The boundaries at the final analysis for Cohort B do not change if no interim analysis is performed.

Operating characteristics (Type I and Type II error) were calculated using the exact binomial distribution and are detailed in the SAP. It can be noted that the futility stopping boundary for both cohorts at the interim and final analyses use the rho family beta-spending boundary with parameter = 3 and that the efficacy stopping boundary for both cohorts at the interim and final analyses use the rho family alpha-spending boundary with parameter = 5.

9.5.2. Interim Safety Assessments

An E-DMC will review cumulative safety data during the study conduct and may make recommendations to alter the conduct of the study (see Section 9.6). In addition, the incidence of Grade 3-4 CRS, Grade 3-4 ICANS, Grade 4 treatment-related non-hematologic events (excluding CRS and ICANS), Grade 3-4 treatment-related GBS/GBS-like AEs, Grade 4 treatment-related peripheral neuropathy/immune-related (IR) neurologic events, and Grade 5 events will each be monitored by the Sponsor throughout the study. If the number of participants observed to have such identified events exceeds a pre-specified threshold, the study will be placed on a temporary enrollment hold by the Sponsor until discussions can be held with the Study Steering Committee and the E-DMC. During any temporary enrollment hold, no new participants can be enrolled, nor can any newly enrolled participant start study intervention. Pending Steering Committee and E-DMC assessment, participants who have already started study intervention may continue treatment only if the benefit/risk assessment for the participant is judged to be positive by the investigator in consultation with the sponsor.

In the event that any criteria for temporary enrollment hold are met, written notification documenting the reason for temporary enrollment hold (or study termination) will be

provided by the sponsor to the investigators, the ECs/IRBs, the regulatory authorities, and any CRO(s) used in the study (see also Section 10.1.8).

The criteria for placing the study on temporary hold for the following safety reasons are based on Bayesian posterior probabilities. Using a non-informative Beta (0.5, 0.5) prior distribution, if the number of participants observed to have Grade 3-4 CRS results in a posterior probability that the true Grade 3-4 CRS rate exceeding 20% is \geq 0.80, the study will be put on a temporary hold. Separate but similar criteria will be used for participants with Grade 3-4 ICANS and treatment-related Grade 4 non-hematologic events (excluding CRS and ICANS). Table 6 summarizes the minimum number of participants with such identified events that would meet the above criteria.

Table 6.Minimum Number of Participants With Identified Events That Would
Prompt Temporary Enrollment Hold (CRS, ICANS, Non-hematologic
treatment-related AEs)

Number of Evaluable Participants (Cohort A + B)	10-13	14-18	19-22	23-26	27-30	31-35	36-39
Minimum number of participants with Grade 3-4 CRS events that would lead to a temporary enrollment hold*	4	5	6	7	8	9	10
Minimum number of participants with Grade 3-4 ICANS events that would lead to a temporary enrollment hold*	4	5	6	7	8	9	10
Minimum number of participants with Grade 4 treatment-related non hematologic events (excluding CRS and ICANS) that would lead to a temporary enrollment hold*	4	5	6	7	8	9	10

Prior distribution: Beta (0.5,0.5)

Criteria for 40 or more evaluable participants will be calculated such that the study will be put on temporary hold if the posterior probability that the true event rate exceeds 20% is ≥ 0.80 .

Evaluable participants are defined as those who have received at least 1 dose of study treatment having an identified event or those without such an event who have been followed for at least 28 days from first dose. * The study will be put on temporary hold as soon as the minimum number of evaluable participants with the identified AEs has reached the threshold (eg, if there are 4 participants experiencing the identified AE out of the first 6 evaluable participants, the study will be put on hold).

The criteria for placing the study on temporary hold for the following safety reasons are based on Bayesian posterior probabilities using a non-informative Beta (0.5, 0.5) prior distribution.

• If the number of evaluable participants observed to have treatment-related Grade 3-4 GBS/GB-like AEs results in a posterior probability that the true rate of such events exceeding 3% is ≥0.80, the study will be put on a temporary hold.

• If the number of evaluable participants observed to have treatment-related Grade 4 sensory neuropathy/other IR neurologic AEs (excluding ICANS) or treatment-related Grade 3-4 motor neuropathy results in a posterior probability that the true rate of such events exceeding 10% is ≥0.80, the study will be put on a temporary hold.

Table 7 summarizes the minimum number of evaluable participants with such identified events that would meet the above criteria. (See also Appendix 13 for additional details.)

Table 7.Minimum Number of Participants With Identified Treatment-Related
Events That Would Prompt Temporary Enrollment Hold (GBS/GB-like
AEs, Peripheral Neuropathy/IR Neurologic AEs)

Number of Evaluable Participants (Cohort A + B)	20-39	40 -64	65-90	91- 116	117- 144	145- 150 ^a	
Minimum number of participants with Grade 3-4 treatment-related GBS/GB-like events that would lead to a temporary enrollment hold*	2	3	4	5	6	7	
Number of Evaluable Participants (Cohort A + B)	20-27	28-35	36-43	44-52	53-60	61-69	70-78 ^b
Minimum number of participants with Grade 4 treatment-related sensory neuropathy /IR neurologic AE (excluding ICANS) or Grade 3-4 treatment-related motor neuropathy events that would lead to a temporary enrollment hold**	4	5	6	7	8	9	10

Prior distribution: Beta (0.5,0.5)

a.Criteria for 151 or more evaluable participants will be calculated such that the study will be put on temporary hold if the posterior probability that the true event rate exceeds 3% is ≥ 0.80 .

b.Criteria for 79 or more evaluable participants will be calculated such that the study will be put on temporary hold if the posterior probability that the true event rate exceeds 10% is ≥ 0.80 .

Evaluable participants are defined as those who have received at least 1 dose of study treatment having an identified event or those without such an event who have been followed for at least 28 days from first dose. *The study will be put on temporary hold as soon as the minimum number of evaluable participants with the

identified AEs has reached the threshold (eg, for GBS/GB-like AEs, if there are 2 participants experiencing the identified AE out of the first 10 evaluable participants, the study will be put on hold).

** The study will be put on temporary hold as soon as the minimum number of evaluable participants with the identified AEs has reached the threshold (eg, if there are 4 participants experiencing the identified AE out of the first 15 evaluable participants, the study will be put on hold).

In addition, the study will be put on temporary hold if any of the following criteria are met:

- 1 Grade 5 event of CRS,
- 1 Grade 5 event of ICANS,
- 1 Grade 5 treatment-related peripheral neuropathy or IR neurologic event,

• Any 2 treatment-related Grade 5 events (excluding CRS and ICANS and peripheral neuropathy/IR neurologic event).

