# 7.1.2. Interim Safety Assessments

An E-DMC will review cumulative safety data during the study conduct and may make recommendations to alter the conduct of the study. In addition, the incidence of Grade 3-4 CRS, Grade 3-4 ICANS, Grade 4 treatment-related non-hematologic events (excluding CRS and ICANS), Grade 3-4 treatment-related GBS/GB-like AEs, Grade 4 treatment-related peripheral neuropathy/immune-related (IR) neurologic events (excluding ICANS), Grade 3-4 treatment-related motor neuropathy, and Grade 5 events will each be monitored throughout the study. If the number of participants observed to have such identified events exceeds a pre-specified threshold, the study will be placed on a temporary enrollment hold by the sponsor until discussions can be held with the E-DMC. During any temporary enrollment hold, no new participants can be enrolled, nor can any newly enrolled participants start study intervention. Pending E-DMC assessment, participants who have already started study intervention may continue treatment only if the benefit/risk assessment for the participant is judged to be positive by the investigator in consultation with the sponsor.

In the event that any criteria for temporary enrollment hold are met, written notification documenting the reason for temporary enrollment hold (or study termination) will be provided by the sponsor to the investigators, the ECs/IRBs, the regulatory authorities, and any CRO(s) used in the study.

The criteria for placing the study on temporary hold for safety reasons are based on Bayesian posterior probabilities. Using a non-informative Beta (0.5, 0.5) prior distribution, if the number of participants observed to have Grade 3-4 CRS results in a posterior probability that the true Grade 3-4 CRS rate exceeding 20% is  $\geq$ 0.80, the study will be put on a temporary

hold. Separate but similar criteria will be used for participants with Grade 3-4 ICANS and treatment-related Grade 4 non-hematologic events (excluding CRS and ICANS). Table 6 summarizes the minimum number of participants with such identified events that would meet the above criteria.

Table 6.	Minimum Number of Participants With Identified Events That Would
	Prompt Temporary Enrollment Hold

Number of Evaluable Participants (Cohort A + B)	10-13	14-18	19-22	23-26	27-30	31-35	36-39
Minimum number of participants with Grade 3-4 CRS events that would lead to a temporary enrollment hold*	4	5	6	7	8	9	10

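### The Table 6 hold count for treatment-related non-hematologic events stops at Grade 4, so a first related death can leave the study one short of a hold that another Grade 4 event would have triggered

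*Protocol*

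**What the plan says.** Protocol 9.5.2 sets up two kinds of temporary enrollment hold.

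- **Rate-based holds.** "Using a non-informative Beta (0.5, 0.5) prior distribution", Grade 3-4 CRS triggers a hold when "the posterior probability that the true event rate exceeds 20% is ≥ 0.80". The text then adds: "Separate but similar criteria will be used for participants with Grade 3-4 ICANS and treatment-related Grade 4 non-hematologic events (excluding CRS and ICANS". The matching Table 6 row is the "Minimum number of participants with Grade 4 treatment-related non hematologic events (excluding CRS and ICANS) that would lead to a temporary enrollment hold". It runs from 4 participants at 10-13 evaluable to 10 at 36-39; beyond that the same criterion is to be calculated.
- **Death-based holds.** One Grade 5 CRS, one Grade 5 ICANS, or one treatment-related Grade 5 peripheral neuropathy or immune-related neurologic event is enough. For all other related deaths the trigger is "Any 2 treatment-related Grade 5 events (excluding CRS and ICANS and peripheral neuropathy/IR neurologic event".

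The denominator is defined in the Table 6 notes. A treated participant with an event of the kind being counted is evaluable straight away; the rest of the denominator is "those without such an event who have been followed for at least 28 days from first dose".

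SAP 7.1.2 carries the same rules. Its rate-based criterion also names "treatment-related Grade 4 non-hematologic events (excluding CRS and ICANS" without Grade 5, and its death-based list has the same two-death clause.

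**The concern.** A rule that estimates the rate of severe related toxicity should not read a worse outcome as less evidence of toxicity. For CRS, ICANS and neurologic events, leaving Grade 5 out of the count does no harm, because the first death holds the study by itself. For the remaining related non-hematologic deaths (infection is the obvious example) the first death triggers nothing on its own and is not in the Table 6 numerator. If one Grade 4 event is replaced by a death, a hold can become no hold.

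What depends on this is the timing of the hold. A hold brings written notification to investigators, ethics committees and regulators. It also means that participants already on treatment continue only on an individual benefit/risk judgment.

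**Working it through.** **Inputs** (Protocol 9.5.2 and Table 6): prior Beta(0.5, 0.5); limit 20%; posterior threshold 0.80; other related deaths, 2 at any number treated. Number treated: 187 (Protocol 2.2.3.2).

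**Formula.** With x participants counted among n evaluable, the posterior is Beta(0.5 + x, 0.5 + n - x). Hold if P(rate > 0.20) is at least 0.80.

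**Step 1: reproduce Table 6.** The smallest x meeting the criterion, for every n from 10 to 39, is 4, 5, 6, 7, 8, 9 and 10 in the seven bands. This matches the table at every n. The same formula gives 42 at n = 187. The thresholds are right for the grades they name; the issue is only what is counted.

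**Step 2: replace one Grade 4 event by a first related death.**

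| Evaluable | Events | Posterior, Grade 4 only | Posterior, Grade 4 or 5 |
|---|---|---|---|
| 13 | 3 Grade 4 + 1 Grade 5 | 3/13: 0.634, no hold | 4/13: 0.837, hold |
| 35 | 8 Grade 4 + 1 Grade 5 | 8/35: 0.676, no hold | 9/35: 0.805, hold |
| 187 | 41 Grade 4 + 1 Grade 5 | 41/187: 0.748, no hold | 42/187: 0.801, hold |

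The next event does not always repair this. If the 14th evaluable participant also has a Grade 4 event, the written count is 4/14 (0.796, no hold) and the pooled count is 5/14 (0.922).

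**Step 3: how far the two-death rule limits the gap.** Two deaths are 2/13 = 15.4%, 2/39 = 5.1% and 2/187 = 1.1% of participants. The Grade 4 trigger is 4/13 = 30.8%, 10/39 = 25.6% and 42/187 = 22.5%. At most one such death can therefore stand uncounted before a hold follows anyway.

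**Step 4: effect on timing.** The documents give no event rates, so these are assumptions. Participants were simulated one at a time with the Table 6 formula extended, a minimum of 4 events, and the two-death rule kept in both versions. A fatal case was never also counted at Grade 4, and trials with no hold by the last participant were set to that number.

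- *Grade 4-or-worse rate 25-30%, of which 10-20% fatal, to n = 60.* The written rule holds later in 25-36% of trials. The mean delay is 6-10 participants among delayed trials and about 2.1-2.6 over all trials. The chance of a hold is 82-97% as written and 85-98% pooled.
- *Same rates, to n = 187.* The chance of a hold is at least 99% either way.
- *Grade 4 rate 10%, Grade 5 rate 1%, to n = 187.* About 2% of trials are delayed. The chance of a hold is 58.6% as written and 58.9% pooled.
- *Grade 4 rate 20%, Grade 5 rate 1%, to n = 187.* The chance of a hold is 83.6% as written and 84.8% pooled.

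**The case against.** The strongest reply is that deaths are not ignored: they have their own, much stricter rule. That is correct. A reader might infer that a fatal event in general counts for less than a life-threatening one. The documents do not support this. The first other related death is half of the two-death trigger, while one Grade 4 event is 1 of 4 at n = 10-13 and 1 of 42 at n = 187; a neurologic death, which is also non-hematologic, holds the study alone.

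Two further inferences also fail.

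- *That a participant who worsens from Grade 4 to Grade 5 leaves the numerator.* Nothing says so. The rule acts as soon as the count is reached and has no worst-grade convention; the SAP uses maximum grade for summary tables. The text is silent, which is a reason to clarify it.
- *That a death before day 28 drops from the denominator and so hides the signal.* Such a participant may meet neither limb of the evaluable definition. But the opening paragraph of 9.5.2 uses the term identified events for a list that includes Grade 5, so the death can be read as evaluable. If it were dropped, the posterior would rise (3/12 = 0.688 against 3/13 = 0.634), which moves toward a hold.

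It also stands that the E-DMC can act on cumulative safety data without any threshold, that serious events reach the sponsor within 24 hours, and that enrollment closed in January 2022. These reduce the consequence. They do not explain why the count should stop at Grade 4 for a class in which one death is not itself a trigger.

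**Conclusion.** The point holds in a narrow form. Outside CRS, ICANS and neurologic events, a first related non-hematologic death adds to the two-death count but not to Table 6. The written rules give a different answer from a pooled count when one such death has occurred and the Grade 4 count is one below its threshold. In that configuration the worse outcome produces no hold where the lesser one would.

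The posteriors in Step 2 follow from the stated prior and limit alone. The timing figures rest on assumed rates and on fatal cases not having been counted first at Grade 4; if some were, the effect is smaller. On those assumptions a sizeable minority of trials hold later at high toxicity, the average delay is about 2 to 2.5 participants, and the overall chance of a hold changes little. With accrual complete, what can still be affected is hold notification and the continuation clause for treated participants. It is worth correcting because the rule is still in force in both current documents and criteria beyond the tabulated range must still be calculated from it.

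**What to change.** In Protocol 9.5.2 (opening paragraph, rule text and third row of Table 6) and the same places in SAP 7.1.2, count participants with treatment-related Grade 4 or 5 non-hematologic events, still excluding CRS and ICANS. Add two statements:

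1. A participant counted at Grade 4 stays counted if the event later becomes fatal.
2. A treatment-related death makes the participant evaluable from the date of the event.

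Leave the Table 6 thresholds and the separate Grade 5 rules as they are; the thresholds depend only on n, the prior, the 20% limit and the 0.80 cut-off. No efficacy analysis changes.

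The cost is a short protocol amendment with a matching SAP update. The amendment history records earlier changes to the hold criteria as regulatory requirements, so this is more than an editorial correction. The operational downside is a slightly earlier temporary hold when one related death has occurred.
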